8.1 Clinical criteria for withdrawing an individual subject from the study

Clinical criteria for withdrawing an individual subject from the study are as follows:

- Subject chooses to withdraw
- The occurrence of an adverse event, which, in the judgment of the Investigator or independent monitor, suggests an unacceptable risk to the subject
- Pregnancy
- Investigator discretion
- Subject noncompliance

8.2 Criteria for stopping or changing the study protocol

Criteria for stopping or changing the study protocol due to safety concerns are as follows:

- Should the investigator, independent monitor, the FDA, or local regulatory authorities become aware of conditions arising during the conduct of this study that may warrant the cessation of the study, such action may be taken. Prior to such action, consultation between the investigator, and, as appropriate, the FDA and/or local regulatory authorities will take place
- If there are >2 subjects with serious adverse events, the independent study
 monitor will examine and audit the cases and determine the relevance to the
 assigned study medical food supplement and whether the trial should continue
 or if there are grounds for discontinuing the study

8.3 Follow-up of AEs and SAEs

All AEs and SAEs must be followed until resolution, until the condition stabilizes, until the event is otherwise explained, or the subject is lost to follow-up. The investigator is responsible to ensure that follow-up includes any supplemental investigations as may be indicated to elucidate as completely as practical the nature and/or causality of the AE or SAE. This may include additional laboratory tests or investigations, histopathological examinations, or consultation with other health care professionals.

8.4 **Prompt Reporting of SAEs to Salix Pharmaceuticals.**

Serious adverse events must be reported promptly to Salix pharmaceuticals. once the investigator determines that the event meets the protocol definition of an SAE.

Prompt reporting of a SAE requires:

- Completion and transmission of SAE information to Salix pharmaceuticals. within 24 hours of the investigator's knowledge of the event. The SAE It is very important that the investigator provide his/her assessment of causality to investigational product at the time of initial reporting of the SAE. SAE information should include at a minimum:
 - AE description (diagnosis)
 - Onset Date

- Resolution date
- Duration
- Seriousness (Fatal, Life Threatening, Hospitalization require or prolonged, Congenital anomaly, Disabling/Incapacitating, Other – describe)
- Contributing factors (underlying disease being studied, concurrent illness
 specify if yes, concurrent therapy specify if yes, other describe)
- List relevant medical conditions (past or current), include onset and resolution dates if known
- List any medications taken to treat this SAE
- Provide any relevant diagnostic procedures and laboratory results
- Add a narrative/comments providing a textual description of the SAE including chronological presentation and evaluation of the SAE, associated signs and symptoms, treatment of the SAE and outcome of the SAE.

Prompt reporting of additional information for previously reported SAEs should follow the same reporting timeframe as initial reports.

8.5 Pregnancy Reporting

Pregnancies detected during study conduct should be promptly reported to Salix pharmaceuticals as soon as the investigator is notified. should be notified via fax of any updates on the status of the pregnancy as soon as the information becomes available by update and/or amendment of the initial pregnancy reporting form. Pregnancies will be followed to term and information will be collected on the pregnancy outcome, including spontaneous or voluntary termination, details of the birth, and the presence or absence of any birth defects, abnormalities, or complications.

9.0 AUDITS

At its discretion, Salix pharmaceuticals may conduct a quality assurance audit of this study. If such an audit occurs, the investigator agrees to allow the auditor direct access to all relevant documents and to schedule his/her time and the time of his/her staff to permit meetings with the auditor to discuss findings and any relevant issues.

In addition, regulatory agencies may conduct a regulatory inspection of this study. If such an inspection occurs, the investigator agrees to allow the inspector direct access to all relevant documents and to schedule his/her time and the time of his/her staff to permit meetings with the auditor to discuss findings and any relevant issues.

11.0 SUPPORT REQUESTED (STUDY BUDGET)

Labor	Cost		Sub	Totals
1. Principal Investigator with fringe (1% effort)	\$	3,248		
2. Co-Investigator with fringe (3% effort)	\$	9,901		
3. Study Coordinator with fringe (19.5% effort)	\$	14,120	\$	27,269
Other Direct Costs	Ì			
1. Lactulose breath tests	\$	11,855		
2. Rectal sensitivity tests	\$	22,902		
3. Pharmacy dispensing fees	\$	1,200		
4. IRB fees (overhead not applicable)	\$	3,000		
5. Pharmacy startup fee	\$	1,500		
6. Pharmacy closeout fee	\$	500		
7. Patient compensation (\$80 per visit x 80 visits)	\$	6,400		
8. Pregnancy tests (for exclusion criteria)*	\$	173	\$	47,530
Direct Cost Total			\$	74,799
Overhead (30%, no overhead on IRB fees)			\$	21,540
Total Initial Budget	ĺ		\$	96,339
Additional Annual Invoiceable Costs**				
1. IRB Continuing Expedited Review Fee (overhead not applicable) † or	\$	750	\$	750
2. IRB Continuing Full Committee Review Fee (overhead not applicable) †	\$	1,500	\$	1,500
3. Pharmacy Annual Renewal Fee (inclusive of 30% overhead)	\$	975	\$	975
Total Study Costs (including one (1) Pharmacy Renewal at \$975 including overhead and One IRB Continuing renewal at the maximum \$1,500 fee).			\$	98,814

* Assuming 50% of subjects are females of childbearing age
 ** Paid only if study extends into second year

† Either the \$750 Continuing Review fee or the \$1500 Continuing Review fee may be charged at annual renewal depending on the type of review the IRB does, but both fees won't be charged for the same review.

Labor	Cost	Sub-Totals
-------	------	------------

1. Principal Investigator with fringe (1% effort)	\$ 3,248	
2. Co-Investigator with fringe (3% effort)	\$ 9,901	
3. Study Coordinator with fringe (19.5% effort)	\$ 14,120	\$ 27,269
Other Direct Costs		
1. Lactulose breath tests	\$ 11,855	
2. Rectal sensitivity tests	\$ 22,902	
3. Pharmacy dispensing fees	\$ 1,200	
4. IRB fees (overhead not applicable)	\$ 3,000	
5. Pharmacy startup fee	\$ 1,500	
6. Pharmacy closeout fee	\$ 500	
7. Patient compensation (\$80 per visit x 80 visits)	\$ 6,400	
8. Pregnancy tests (for exclusion criteria)*	\$ 173	\$ 47,530
Direct Cost Total		\$ 74,799
Overhead (30%, no overhead on IRB fees)		\$ 21,540
Total Initial Budget		\$ 96,339
Additional Annual Invoiceable Costs**		
 IRB Continuing Expedited Review Fee (overhead not applicable) † or 	\$ 750	\$ 750
5. IRB Continuing Full Committee Review Fee (overhead not applicable) †	\$ 1,500	\$ 1,500
6. Pharmacy Annual Renewal Fee (inclusive of 30% overhead)	\$ 975	\$ 975
Total Study Costs (including one (1) Pharmacy Renewal at \$975 including overhead and One IRB Continuing renewal at the maximum \$1,500 fee).		\$ 98,814

* Assuming 50% of subjects are females of childbearing age
** Paid only if study extends into second year
† Either the \$750 Continuing Review fee or the \$1500 Continuing Review fee may be charged at annual renewal depending on the type of review the IRB does, but both fees won't be charged for the same review.

Appendix 1: Baseline Questionnaire

Patient Code: _____

SECTION 1: DEMOGRAPHICS

- 1. Date:_____
- 2. Age: _____
- 3. Sex: _____
- 4. Height: _____
- 5. Weight (lbs): _____

SECTION 2: PAST MEDICAL AND SURGICAL HISTORY

1. In the following chart answer yes or no to the surgeries listed and list any other previous surgical procedures you have had:

PLEASE PRINT CLEARLY

Type of Surgery	Circle YES or NO		Problem (symptoms)	Date of Surgery
1. Appendix removal	YES	NO		
2. Tonsils removal	YES	NO		
3. Gastric Bypass	YES	NO		
4.				
5.				
6.				
7.				
8.				
9.				
10.				

(If more than 10 surgical procedures...continue on reverse of this page)

2. Please indicate if you have ever been told you have any of the following diagnoses:

Diagnosis	Indicate "X" if you have been told you had the diagnosis	If yes, when was it diagnosed?
1. Irritable bowel		
2. Crohn's Disease		
3. Ulcerative Colitis		
4. Fibromyalgia		
5. Gastroesophageal reflux disease		
6. Diabetes (Type I)		
7. Diabetes (Type II)		

FOR WOMEN ONLY:

Do you have a history of difficultly getting pregnant?	YES	NO
Do you have irregular periods?	YES	NO
Have you ever been diagnosed with polycystic ovary syndrome (PCOS)?	YES	NO

SECTION 3: MEDICATIONS

1. List the medications that you are on currently:

PLEASE PRINT CLEARLY

Medication	Dose	For what problem	Approximate start date
1.			
2.			
3.			
4.			
5.			
6.			
7.			
8.			
9.			
10.			

(If more than 10...continue on reverse of this page)

2. List any antibiotics other than rifaximin you have taken in the last 6 months:

Antibiotic	Dates taken	Why taken?
1.		
2.		
3.		
4.		
5.		

SECTION 4: SOCIAL HISTORY

1. Do you or did you ever smoke? If "YES", when did you sta and when did you o	YES art quit		0
2. Do you drink alcohol? If "YES", you drink every (day/week/	YES _ glasses of month)	N (type of a	O Icohol)
3. Were you breastfed as a child? If "YES", for how long	YES ?	NO	Unknown

SECTION 5: TRAVEL HISTORY

1. In the following chart, list the places outside of the US you have traveled:

Location Traveled	Date	Did you experience excessive Diarrhea on this trip?	
1.		YES NO	
2.		YES NO	
3.		YES NO	
4.		YES NO	
5.		YES NO	
6.		YES NO	
7.		YES NO	
8.		YES NO	
9.		YES NO	
10.		YES NO	

(If more than 10...continue on reverse of this page)

SECTION 6: DIETARY CHANGES

1. Please list any recent changes you have made to your diet:

Date started	Type of Change	Date discontinued (if applicable)
1.		
2.		
3.		
4.		
5.		
6.		
7.		
8.		
9.		
10.		

Appendix 2: Lactulose Breath Test

Preparation for the Test:

Subjects will not be allowed to consume any heavy protein or legumes on the night before the test.

Subjects will fast beginning at 7 pm on the previous evening to guarantee a 12 hour fast. Only water will be allowed until midnight before the test. Subjects cannot chew gum during this time of fasting.

All subjects will be asked to brush their teeth or use mouthwash (not swallowed) and refrain from smoking cigarettes on the morning of the test.

Test Administration:

All subjects will provide a baseline end expiratory breath sample at the start of the test.

They will then be provided a syrup containing 10 g of lactulose syrup after which breath samples will be collected every 15 minutes exactly for 120 minutes.

Sample Analysis:

Samples will be analyzed using a gas chromatograph capable of measuring hydrogen (H₂), methane (CH₄) and carbon dioxide (CO₂). The CO₂ will be used to correct for alveolar sampling error. The H₂ and CH₄ will be plotted on a graph with time on the x-axis and gas concentration in ppm on the y-axis.

Appendix 3: Stool Diary

See next page.

Daily Diary		Subject Number:	
If you had no bowel movements today, please check this box:			
	Describe the consistency of bowel movement	Describe the Ease of Passage of bowel movement	Did you feel like you completely emptied your bowels?
Date:// 20	 hard lumps lumpy sausage cracked sausage smooth sausage soft lumps mushy watery 	 no straining needed mild straining moderate straining severe straining very severe straining 	n 1 o 2 yes
1 hr. min pm			
2 hr. min pm			
3 am			
4 am am am pm			

(If more than 4...continue on reverse of this page)

Bristol Stool Chart

Type 1		Separate hard lumps, like nuts (hard to pass)
Type 2	6539	Sausage-shaped but lumpy
Туре 3		Like a sausage but with cracks on the surface
Туре 4		Like a sausage or snake, smooth and soft
Туре 5		Soft blobs with clear-cut edges
Туре б		Fluffy pieces with ragged edges, a mushy stool
Туре 7	Ś	Watery, no solid pieces. Entirely Liquid

Appendix 5: Assessment of rectal sensitivity using graded balloon distention

A standard non-latex rectal balloon (Mui Scientific, Mississauga, Ontario, Canada) will used for assessment of rectal sensitivity. After lubrication the balloon will be inserted into the rectum and will be advanced for 5 cm. The balloon will be inflated by 20 cc and pull back until sphincter resistance is appreciated. At this point the catheter will be advance 3cm and will be deflated. Following a 20 second hiatal, every minute the balloon will be inflated by 10 cc in 10 seconds. Patient will be asked about the sensation after 10 seconds. Patients will be blinded from the balloon volume or whether the balloon is inflated. The balloon will be deflated and inflated with 10cc incremental volumes until the first sensation, first sensation of urge, normal sensation of urge and severe sensation of urge is appreciated (see scale below). When these points are achieved, the balloon pressure will also be recorded (Posey 8199 Manometer, Arcadia, CA, USA). The maximum inflated volume will be 200 cc.

0- No sensation: No fullness is sensed in the rectum

20- First sensation: Feeling fullness in the rectum but no urge (would not go or plan to go to restroom)

40- First sense of urge to defecate: Sensation of fullness and mild urge to defecate (would not go to bathroom)

60- Normal urge to defecate: Usual sensation of urge to defecate (would plan to go restroom but would not rush)

80- Severe urge to defecate: Would stop any non-essential activity and rush to a bathroom.

100- Pain: Sensation of pain/discomfort different from urge.

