1.2 Current Standard Therapy

Currently, three drugs for IBS-D (rifaximin, alosetron and eluxadoline) and two (linaclotide and lubiprostone) for IBS-C are approved by FDA ¹⁹. While these drugs have shown to decrease abdominal pain based on subjective scales in their respective clinical trials, there is very little data to substantiate objective changes in visceral hypersensitivity. While rifaximin is an

5

antibiotic, the exact underlying mechanism of action for rifaximin in reducing the pain component of IBS remains unknown. However, rifaximin is the only medication that has been shown in randomized controlled trials to decrease abdominal discomfort in all subtypes of IBS. This suggests that rifaximin, unlike other approved medications, addresses the underlying pathophysiology of IBS rather than simply targeting symptom relief.

Given the role of altered bacterial populations in IBS, a number of randomized controlled trials have been conducted examining the utility of antibiotics in treating IBS ²⁰⁻²³. All of these controlled trials have demonstrated significant success with antibiotic therapy. The two principal antibiotics studied to date are neomycin ⁸ and rifaximin (Xifaxan) ^{21, 24, 25}. While neomycin was a successful therapy for IBS, it was disappointing in its ability to normalize the lactulose breath test (LBT) ⁸. In contrast rifaximin, a non-absorbed antibiotic (99.6% retained in the GI tract), has been shown to normalize the LBT in 70% of subjects ²⁶. The most recent phase III randomized controlled trial of rifaximin demonstrated three important findings ²³:

First, rifaximin was effective in improving the primary endpoint (adequate relief of global IBS symptoms and newer FDA endpoints for IBS) compared to placebo. Second, rifaximin treatment resulted in significantly greater improvement in all major IBS symptoms (abdominal pain, bloating, and stool consistency). Third, the drug had a durable effect for over 3 months after the cessation of therapy²³.

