6.2 Therapy phase

If patients meet the inclusion criteria and provide informed written consent, they will:

Visit 1: Day -7	-	Undergo a urine pregnancy test (if a woman of childbearing potential)
	-	Complete a baseline symptom questionnaire (see Appendix 1).
		This can either be filled online using REDCap, a secure, web-
		based application for building and managing online surveys and
		databases with which Cedars-Sinai is partnered, or completed in paper format
	-	Present fasting for a full lactulose breath test (see Appendix 2)
	-	Up to 60 cc of exhaled breath gas at baseline and 120 minutes of
		testing will be stored for additional testing by mass spectroscopy
		(Exetainer® 12ml flat-bottom vacuumed vials, LabCo, UK).
	-	Subjects will be given a stool diary (see Appendix 3) and asked to
		complete this at home over the next 7 days, using the Bristol Stool
		Chart (see Appendix 4) as a visual aid
	-	Patient will undergo a rectal sensitivity assessment (Appendix 5)
Day -7 to Day 0	-	Complete a 7-day baseline stool and symptom diary (see

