 Appendix 6) at home, beginning on Days 0 and 7. Again, these
 can either be filled online using REDCap, or completed in paper

 format
 - Subjects will complete a Daily Stool Diary (see Appendix 3)
- *Visit 2: Day 15* Subject will undergo a rectal sensitivity assessment (Appendix 5)
 - Subject will undergo an LBT
 - Up to 60 cc of exhaled breath gas at baseline and 120 minutes of testing will be stored for additional testing by mass spectroscopy (Exetainer® 12ml flat bottom vials, LabCo, UK).

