7.0 OUTCOME MEASURES

7.1 Primary Outcome Measure

The primary outcome of the study is the mean change in the balloon volume that leads to first urge to defecate. A 100-mm visual analogue scale with verbal descriptors (0=no sensation, 20=first sensation, 40=first sense of urge, 60=normal urge to defecate, 80=severe urge to defecate, and 100=discomfort/pain) will be used to score evoked sensations ³⁰.

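### Appendix 5 neither standardises nor records rectal content before the two balloon tests, so a change in rectal stool between Day -7 and Day 15 could be read as a change in the volume at first urge

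*Combined protocol and SAP*

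**What the plan says.** Section 7.1 defines the endpoint: "The primary outcome of the study is the mean change in the balloon volume that leads to first urge to defecate". Section 6.2 schedules the balloon test at the Day -7 visit and again on Day 15, both times by pointing to Appendix 5.

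Appendix 5 is a detailed procedure. It fixes insertion depth, positioning against the sphincter, a pause before inflation, the inflation rate and the moment at which the subject is questioned. Its first action is "After lubrication the balloon will be inserted into the rectum and will be advanced for 5 cm", and the thresholds are then found stepwise: "The balloon will be deflated and inflated with 10cc incremental volumes until the first sensation". It contains no attempt at emptying, no check for stool and no entry for the last bowel movement. The breath test in Appendix 2, by contrast, has its own preparation instructions.

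On the drug's effect on stool, section 1.2 reports from an earlier phase III trial that "rifaximin treatment resulted in significantly greater improvement in all major IBS symptoms (abdominal pain, bloating, and stool consistency" was seen.

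On the diary, section 6.2 says at the Day -7 visit: "Subjects will be given a stool diary (see Appendix 3) and asked to" fill it in over the following week. It is continued during treatment, Day 0 to Day 14: "Subjects will complete a Daily Stool Diary (see Appendix 3". Appendix 3 shows that each movement is logged with its time, consistency, ease of passage and completeness.

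Section 3.3 plans a paired t test on the before/after change, with no covariate. There is no control arm (section 3.1).

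**The concern.** The endpoint is the volume put into the balloon, not the total volume in the rectum when urge is felt. Stool already present may supply part of the stimulus, so the recorded threshold may reflect rectal content as well as sensitivity. If content varies at random between visits, it adds noise to the paired difference. If it changes on average between the visits, the mean change moves by a corresponding amount. In a single-arm design with an unadjusted paired t test, nothing separates that shift from a change in sensitivity.

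A systematic change is plausible because subjects have IBS-D or IBS-M and the protocol itself says that the drug alters stool consistency. Less stool at Day 15 would look like benefit; more would mask it. What is at stake is whether a positive result, or a null one, can be attributed to rectal sensitivity, which is the stated primary objective. The state of the rectum at the baseline test cannot be reliably reconstructed once that test has been done.

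**Working it through.** **Inputs from section 3.3.** Change of interest 20 cc; effect size 0.50; SD of the urge volume 42 cc; 34 evaluable subjects; power 0.8; Type I error 0.05 (sidedness not stated); dropout 15%; paired t test.

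**Reproducing the plan's figure.** Power of a two-sided paired t test comes from the noncentral t distribution with n − 1 degrees of freedom and noncentrality (mean change / SD of change) × √n. With effect size 0.50 the smallest n for power 0.80 is 34 (power 0.808), and 34 / 0.85 = 40. Both stated figures reproduce. The effect size implies an SD of change of 20 / 0.50 = 40 cc. The 42 cc is a between-patient SD and is used below only as one more value in the range.

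**Illustration: sensitivity unchanged, content shifts.** The documents give no size for a stool effect. Assume that 1 cc of stool displaces 1 cc of balloon volume at urge, and that mean rectal content falls by *b* cc between the tests. The paired t test then sees a mean change of *b*, with noncentrality (*b* / SD) × √34. For *b* = 10 cc, which is one inflation step, and SD 40 cc this is 0.25 × 5.831 = 1.458. The critical value is 2.0345 on 33 degrees of freedom.

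Proportion of trials with p<0.05:

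| Assumed mean shift | SD 30 cc | SD 40 cc | SD 42 cc | SD 50 cc |
|---|---|---|---|---|
| 0 cc | 5% | 5% | 5% | 5% |
| 5 cc | 16% | 11% | 10% | 9% |
| 10 cc | 47% | 29% | 27% | 21% |

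For scale, the smallest mean change that reaches significance at SD 40 cc is 2.0345 × 40 / √34 ≈ 14 cc.

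**Opposite direction.** If the true gain is 20 cc and content rises by *b*, the observed mean is 20 − *b*. At SD 40 cc, power falls from 0.81 to 0.56 for *b* = 5 cc (mean 15 cc) and to 0.29 for *b* = 10 cc (mean 10 cc).

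**Noise only.** If content adds independent random error with an assumed SD of 10 cc at each visit, the SD of change becomes √(40² + 2 × 10²) = 42.4 cc. Power at n = 34 falls to 0.76, and 38 subjects would be needed for 0.80.

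**What the diary can recover.**
- Baseline test (Day -7): the diary is issued at that same visit for later completion, so the preceding movement is not recorded.
- Day 15 test: entries run to Day 14, so the last movement is largely recoverable, apart from any on the morning of the test.
- Stool pattern: covered for the pre-treatment week and through treatment.

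An adjustment for time since the last movement needs the value at both tests, and only one is partly available. No planned analysis links the diary to the balloon result.

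**The case against.** The strongest reply is that no bias has been shown. Section 1.2 speaks of consistency, not of the amount of stool in the rectum at a test, and the step from one to the other is an inference. This stands. A reader might infer that the primary result will be driven by a treatment-related change in stool; the documents do not support that, because they give neither size nor direction. The displacement ratio, the shifts and the SDs other than 40 and 42 cc are assumptions, which is why a range is shown on both sides of 40 cc.

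Second, the diary is not useless. It documents stool pattern before and during treatment, and a drug-related change in pattern could be set against the change in threshold. So it would go too far to say that nothing could be examined afterwards. What remains missing is the state at the baseline test.

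Third, there are partial safeguards. Both tests share a visit with a fasting breath test, constipation and known pelvic floor dysfunction are excluded, and balloon pressure is recorded as well as volume. The exclusions make retained firm stool less likely. None of these standardises rectal content, and the order of the balloon and breath tests within a visit is not fixed.

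Fourth, the site may already ask subjects to void. If so, the protocol neither requires nor records it, so nobody could confirm that the two tests were done alike.

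Fifth, the remedy is imperfect: an attempt to empty may fail, and hours since the last movement is only a proxy. This also stands and limits what the sensitivity analysis can show.

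**Conclusion.** The point holds as an uncontrolled source of possible bias in the primary endpoint. Rectal content is neither standardised nor recorded before either test, and the single-arm, unadjusted analysis would carry any systematic change in it into the estimate. The size and direction are unknown. On the assumptions stated, a 5 cc mean shift raises the chance of a false positive from 5% to about 9% to 16%, and a 10 cc shift to about 21% to 47%, with the higher figures belonging to the smaller SD of change. An opposite shift would conceal benefit to a comparable degree, and purely random variation would cost only modest power in the case computed. These figures show how sensitive the design is; they do not predict what will happen. The change is worth making because it is cheap and has to be in place before the baseline tests are done.

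**What to change.** At the start of Appendix 5, add a preparation step that is identical at Day -7 and Day 15: the subject attempts to empty the bowel on site before the test, and the time and Bristol type of the last bowel movement are written on the test sheet.

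In section 3.3, add one sensitivity analysis of the primary change, adjusted for the between-visit difference in time since the last bowel movement. State that this variable is only a proxy for rectal content. The paired t test stays primary.

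Do not restrict an analysis to subjects with an empty rectum at both tests. That selects on a variable measured after treatment and shrinks a sample planned at 34.

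The cost is a few minutes per visit and one extra worksheet line, with no additional procedure. The limitation is that a voiding attempt makes the two tests more alike but does not guarantee that the rectum is empty.
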